Informed Consent ^g	X														
Questionnaire	X		X ^b				X ^c							X ^d	
Interviews (SSI)	X		X ^b				Xc							X ^d	
CQI Calls ^e		X	Initial SWAT	X	X	X	X	X	X						
SWAT ^f		X	Meeting and Intro to CQI												
FRAME-IS	X			X	X	X	X	X	X	X	X	X	X	X	
CSAT	X													X	
Provider Toolkit ^h	X		X	X	X	X	X	X	X	X	X	X	X	X	X

Table 2 Schedule of Assessments Table for Staff Study Participants

a) Month 1 starts at site activation

b) Questionnaire and interview should be conducted prior to the site's first patient receiving their first CAB LA + RPV LA injection at that site.

c) Questionnaire and interview should be conducted within approximately 4 weeks of the site's first patient receiving their third injection.

d) Questionnaire and interviews should be conducted within approximately 4 weeks of the site's first patient receiving their last injection.

e) Intro to CQI calls will occur within four weeks of site activation. Additional CQI calls will be scheduled if deemed necessary.

f)Initial SWAT meeting will occur within four weeks of site activation. Additional SWAT meetings with each site will occur as needed throughout the study.

g) Informed consent will be obtained prior to any study assessments (where applicable, as determined by local regulatory and compliance requirements).

h) At a minimum the study toolkit will be offered at the time pointed noted in the Table 6. However, the toolkit items are intended to be used throughout the study.

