1. Investigator Meeting: All site principal investigators and key staff will attend the investigator meeting that will provide information on effectiveness of CAB LA + RPV LA, study procedures, and an overview of safety information.

TMF-13794092

CONFIDENTIAL

- 2. SWAT Meeting with sponsor team and principle clinic stakeholders: This meeting will occur following the investigator meeting, ideally within the first month of the study. At this meeting, site-specific key personnel (e.g., staff study participants, local leadership, administrators, clinical staff) will work with the SWAT to review the Implementation Slide kit and spend time discussing the rationale for CQI and how it will be used to support implementation in the study. Participants in the CQI calls (2 personnel per site) will be identified and confirmed at this time. Participants for the SWAT meeting will be discussed with the site principal investigator to ensure appropriate people from each site are invited to participate in this meeting.
- 3. On-demand SWAT meeting: On request, sites will have access to a follow-up SWAT meeting in person to discuss concerns and/or questions about implementation of CAB LA +RPV LA.
- 4. Monthly Continuous Quality Improvement (CQI) calls: Sites within each country cluster randomized to this condition will attend monthly 1-hour CQI calls together if available. If possible, the key staff at each clinic that participate in the day-to-day injections, medical oversight, and management of CAB LA + RPV LA will attend this call, but a maximum of 2 staff from each site will be included on the calls. This will be determined using information gathered during site selection and confirmed at the initial SWAT meeting. If a barrier is identified that requires an additional staff member attend a CQI call(s), this will be considered on a case by case basis. These calls will be led by a CQI trained leader. During each call, study staff participants will be asked to identify barriers to implementing CAB LA + RPV LA that they identify and work through a Plan, Do, Study, Act (PDSA) cycle on the call. They will then be asked to act on the PDSA cycle between CQI calls to test the success of their strategy at addressing the identified barriers.

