- 5. Face-to-Face injection training: Each site will be provided to an initial face-to-face injection training with the option of adding on virtual injection trainings if requested by the site during the study. Where new staff join the study the injection training should also be provided face-to-face where possible.
- 6. Monthly FRAME assessment: each month the key stakeholder(s) from each site will be asked whether they made any adaptations to the implementation strategies at their site to assist in implementation of CAB LA + RPV LA. This measurement will also be used to capture additional implementation strategies that were not identified by the study team.
- 7. Access to toolkit: All sites will have access to both patient level and HCP level toolkits. See Table 6 for list of anticipated toolkit components.
- 8. Medical science liaison or CAB + RPV Medical Lead will visit each clinic per standard practice in the country.

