4.2.4.2. Standard Implementation Arm (arm-s) Description

Following the investigator meeting each site will have a visit with either a medical science liaison or a medical lead (depending on the country) to address investigational product questions. This might include, but is not limited to, discussing the treatment, answering medical questions, and utilization of toolkits components. On-demand visits or calls with a medical representative will be available. Injection trainings will be conducted virtually at the start of the study, with additional training options available as

needed. To capture and understand a site's successful implementation on their own doing a monthly FRAME-IS will be completed by key stakeholders and are intended to capture current successes and barriers. Of note, this condition will not have access to the country specific implementation strategies developed for arm-e.

The Arm-s will contain the following components:

- 1. Investigator meeting: All site principal investigators and key staff (e.g., nurse, pharmacist) will attend the investigator meeting that will provide information on effectiveness of CAB LA+ RPV LA, study procedures, and an overview of safety information.
- 2. Medical science liaison or CAB + RPV Medical Lead will visit each clinic per standard practice in the country. These meetings will happen quarterly or at the discretion of the clinic. At this meeting, there will be the option of using the Implementation Slide kit, however, it is not a required part of this arm and is to be decided at the discretion of the Lead.
- 3. Access to toolkit component: All sites will have access to both patient level and HCP level toolkits components. See Table 6 for list of anticipated toolkit items.
- 4. Virtual injection training: All sites will have access to a virtual injection training at the start of the study and as needed throughout the study.
- 5. Monthly FRAME assessment: each month the key stakeholder(s) for each site will identify whether they made any adaptations to the implementation strategies at their site to assist in implementation of CAB LA + RPV LA.

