Materials	Objective	Target Audience	Timepoint Offered for Patients and Assessed by Providers
Patient Education materials – Hard copy	Patient Education	Patient	Oral Lead-in, Doses 1- 3, 5
Web-based treatment planner	Scheduling	Staff	Month 1, 2, 4, 6, 8 10
Capacity Planning Tool	Sustainability	Staff	Month 4, 6, 8, 10
Implementation Slide kit	Staff Education/ Capacity Planning	Staff	SWAT meeting or MSL meetings
Patient video	Patient Education	Patient	Oral Lead-in, Dose 1
Injection Training Video	Nurse/Injector Education	Staff/Nurse or Injector	Prior to first injection, throughout the study as needed
In-person Injection Training	Nurse/Injector Education	Enhanced Arm only - Staff/Nurse or Injector	Prior to first injection, throughout the study as needed
Peer to Peer Education	Provider/ Physician Education	Physicians/staff	During enrollment, throughout study as needed
Chatbot	Appointment Adherence and FAQs	Patients (offered at some locations)	Oral Lead-in-End of Study

* Specific toolkits offered in the study will be flexible to ensure the study is offering toolkits consistent what the toolkits that are intended to be offered in routine care.

While a "toolkit" of supporting elements will be provided in this study, clinical sites will be allowed to choose how they will implement CAB LA + RPV LA delivery in their clinical setting (i.e. nurse visit during clinic hours, pre-post clinic hours, weekend hours, Tues/Thursday clinics, in hospital settings, in pharmacies, at home etc.) as well as to create and use their own clinic-developed resources. The delivery models chosen will be tracked by study staff and captured in the questionnaires and SSIs. Modifications made to the implementation process or approach during the study, e.g. who administers the injection, timing of delivery of the injection, use of support materials, etc. are permissible and encouraged in order to facilitate successful delivery of the CAB LA + RPV LA regimen. Investigators will inform the study team of their change and document the reasons why, which will be formally captured by the FRAME-IS in both conditions.

Staff Qualitative Staff Interviews and Quantitative Questionnaires:

Questionnaires and interviews will be administered to the staff study participants at three timepoints:

- Month 1 (established by site activation): Before the first patient receives the first injections at the site
- Month 5: within 4 weeks of the first patient receiving dose 3 at the site.

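### The staff baseline has no set order relative to either arm's start-up activities, so a change-from-baseline or baseline-adjusted contrast could be biased by a net shift between arms

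*Protocol*

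**What the plan says.** **Baseline.** Protocol Table 2, footnote b: "Questionnaire and interview should be conducted prior to the site's first patient receiving their first CAB LA + RPV LA injection at that site". Sections 4.2.5 and 8.2.2 repeat this limit. Table 2 and Section 4.2.5 also label the assessment Month 1, which starts at site activation.

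**Arm-e start-up.** Table 2 places the SWAT meeting and the CQI introduction in the same Month 1 column: "Initial SWAT meeting will occur within four weeks of site activation" and "Intro to CQI calls will occur within four weeks of site activation". Section 4.2.4.1 words the SWAT timing less firmly: "This meeting will occur following the investigator meeting, ideally within the first month of the study". The staff who fill in the questionnaire are among those attending: "At this meeting, site-specific key personnel (e.g., staff study participants, local leadership, administrators, clinical staff) will work with the SWAT". On training, "Each site will be provided to an initial face-to-face injection training", and Table 6 gives the timing of the enhanced-arm-only in-person training as "Prior to first injection, throughout the study as needed".

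**Arm-s start-up.** Section 4.2.4.2: "Injection trainings will be conducted virtually at the start of the study". A medical science liaison or medical lead also visits each site after the investigator meeting and may use the Implementation Slide kit. Liaison or lead visits are listed for arm-e too.

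**Tested quantity.** The Synopsis, the Section 3 table and the row label in Section 9.4.1 word the primary endpoint as change in AIM, IAM and FIM, and the provider precision calculation in Section 9.2 uses change from baseline. The hypothesis in Section 9.1, the power table (Table 11) and the comparison sentence in Section 9.4.1 concern mean scores. SAP Section 2.4 leaves the detail to a separate staff SAP.

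**The concern.** A baseline that serves as the reference for a between-arm change should precede whatever differs between the arms. Here no rule requires that. A site can follow the protocol fully and collect its baseline after staff have attended the SWAT meeting or been trained, so part of the strategy's effect may already be in the baseline.

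The direction cannot be predicted. Early support could raise arm-e scores and pull a change contrast towards no difference. Meetings devoted to finding barriers could lower them and inflate it. Staff are unblinded, and the Month 1 items ask about expectations, so knowing the allocation could itself move answers. At stake is the interpretation of the primary comparison, if that comparison uses the baseline.

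**Working it through.** **1. Timing.** Inputs: screening of up to 35 days (Synopsis), an oral lead-in of about one month (Section 4.1), SWAT meeting and CQI introduction within four weeks of activation (Table 2). Assumption: the first patient is screened on activation day.
- First injection: 0 to 35 days of screening + 30 days of lead-in = day 30 to 65.
- SWAT meeting and CQI introduction: any day up to day 28.
- With the baseline held to a nominal 30-day Month 1, the gap after the day-28 limit is only 30 − 28 = 2 days. The SWAT meeting or training may, however, take place at any earlier point in that month, so the order is still open.

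**2. Bias.** Let D be the true Month 12 difference (arm-e minus arm-s), s the net baseline shift (arm-e shift minus arm-s shift) and b the slope of Month 12 score on baseline.
- Change from baseline: D − s
- Baseline-adjusted: D − b·s
- Month 12 mean: D

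Equal shifts give s = 0 and no bias. Simulation with D = 0.5, b = 0.5 (change / adjusted / Month 12): s = +0.2 gives 0.300 / 0.399 / 0.499; s = −0.2 gives 0.700 / 0.599 / 0.499.

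**3. The plan's own figures.** Two-sided t-test (noncentral t), alpha 0.05, difference 0.5, SDs 0.61 / 0.59 / 0.71 from Table 10:
- 27 per arm: 84.0 / 86.3 / 71.9% (Table 11: 84 / 86 / 72%)
- 36 per arm: 92.9 / 94.4 / 83.8% (Table 11: 93 / 94 / 84%)

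**4. Illustration.** The shift s and the baseline-to-Month 12 correlation rho are assumptions with no source in the documents. SD of change = SD × √(2(1 − rho)); at rho = 0.5 this equals the single-time SD. With equal SDs at both times, b = rho. 27 per arm, no clustering, D = 0.5.

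| s | Change | Adjusted | Month 12 | Power of change contrast, AIM/IAM/FIM |
|---|---|---|---|---|
| −0.25 | 0.75 | 0.625 | 0.50 | 99.3/99.6/96.8% |
| −0.125 | 0.625 | 0.5625 | 0.50 | 95.9/96.9/88.8% |
| −0.05 | 0.55 | 0.525 | 0.50 | 90.2/91.9/79.8% |
| 0 | 0.50 | 0.50 | 0.50 | 84.0/86.3/71.9% |
| +0.05 | 0.45 | 0.475 | 0.50 | 75.8/78.5/62.8% |
| +0.125 | 0.375 | 0.4375 | 0.50 | 60.1/63.0/47.8% |
| +0.25 | 0.25 | 0.375 | 0.50 | 31.5/33.3/24.6% |

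The gains at negative s are spurious. With D = 0, a net shift of 0.05, 0.125 or 0.25 in either direction gives two-sided false-positive rates of 6.0/6.1/5.7%, 11.5/11.9/9.7% and 31.5/33.3/24.6%.

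**5. Sensitivity to rho**, at s = +0.125 (power with no shift in brackets):
- rho 0.3: 46.6/49.1/36.3% (70.5/73.3/57.4%); false positives 9.6/9.9/8.4%
- rho 0.7: 81.6/84.1/69.1% (96.8/97.6/90.6%); false positives 15.9/16.7/13.0%

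**The case against.** The strongest reply is that the stated test concerns mean scores. Sections 9.1 and 9.4.1 say so, and Table 11 is built on score levels and single-time SDs. A comparison of Month 12 means would satisfy that hypothesis and would be untouched. This stands as a limit on the point. It does not remove it, because the endpoint is labelled as change and the staff SAP that would settle the matter was not supplied.

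Other replies stand in part. Arm-s has early activities of its own, and the schema shows the liaison contact where arm-e has SWAT and CQI, so the shifts may partly cancel. The larger figures need a net shift of 0.25, half the design effect, before any injection.

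A reader might infer three stronger things, and the documents support none of them:
- **That the baseline was taken after the arm-e activities.** The schema text lists SWAT/CQI or liaison contact ahead of the baseline survey, but the figure is not shown and no rule requires that order. Compliant baselines may also come first.
- **That the trial is biased towards no difference.** Neither the sign nor the size of any net shift is known.
- **That the baseline may slip to about day 65.** That reading ignores the Month 1 label.

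**Conclusion.** The gap in the schedule is real: no provision puts the staff baseline before either arm's start-up activities, and the SWAT meeting and CQI introduction share its month. Bias itself is not demonstrated. It would need baselines actually taken after these activities, unequal shifts between arms, and an analysis that subtracts or adjusts for baseline. If all three held, the bias would be −s for change and −b·s for the adjusted contrast.

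On the assumed values, a net shift of 0.05 leaves false positives near 6% but moves power by about 6 to 9 points; a shift of 0.125 costs about 23 to 24 points of power when arm-e is raised, and roughly doubles the false-positive rate (rho 0.5). These figures rest on assumed shifts and correlations and on independent observations. The point is a cheap improvement worth making, held with medium confidence because the staff SAP may already fix the contrast.

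**What to change.** **Order.** Amend Table 2 footnote b and Sections 4.2.5 and 8.2.2. For staff enrolled at start-up, the baseline questionnaire is completed before the site's first post-randomisation implementation activity in either arm: SWAT meeting, CQI introduction, liaison or lead visit, slide kit, or injection training in person or virtual. Ideally it also precedes disclosure of the site's allocation. The arm-s liaison or lead visit must be on the list; otherwise arm-e baselines would have to precede SWAT while arm-s baselines could follow its counterpart, and the rule itself would create unequal exposure. The interview may follow the same order where practical, but the quantitative contrast does not need it.

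**Dates.** Record the baseline date and the dates of these activities in both arms.

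**Tested quantity.** State one in Section 9.4.1 and in the staff SAP before arm results are seen. If the order cannot be assured, for example because baselines are already collected, test the Month 12 mean score between arms at all sites, without baseline subtraction or adjustment. This agrees with Section 9.1. Report change from baseline descriptively. Replacement staff (Section 4.3.2) and permitted timing changes (Section 4.2.5) should not alter the tested quantity.

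**Cost.** A 15-minute questionnaire moves earlier, start-up scheduling is slightly tighter, and a few sentences are added. The fallback gives up any precision from baseline adjustment and departs from the labelled change-from-baseline contrast.

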2. INTRODUCTION

2.1. Study Rationale

Cabotegravir long-acting + rilpivirine long-acting (CAB LA + RPV LA) is an investigational HIV-1 treatment regimen administered as two individual intramuscular injections every two months (following an oral lead-in [OLI] period).

The overall objective of the CAB LA + RPV LA clinical development program is to develop a highly effective, well-tolerated, two-drug, long-acting injectable regimen which has the potential to offer improved treatment convenience, compliance and improved quality of life for people living with HIV (PLHIV) compared to current standard of care.

This new HIV treatment will require changes to the current standard of prescribing oral antiretroviral therapies to prescribing and delivering a complete antiretroviral long-acting injectable regimen. As this is a new treatment modality, it is important to understand how to optimize the delivery of CAB LA + RPV LA from a patient, healthcare provider and healthcare system perspective in order to implement into routine care with fewer obstacles. Each country's healthcare system has its own challenges and nuanced differences in the delivery of HIV care. Strategies to support the unique and dynamic contexts for CAB LA + RPV LA implementation is key. As a result, this research study will examine different implementation strategies in different clinics settings across European countries to identify which strategies best meet the needs in each local context. The research in this study will involve both patients receiving the study treatment CAB LA + RPV LA (patient study participants, PSP) as well as the healthcare providers at the investigator site level (staff study participants, SSP).

For PSPs, the study is single-arm, unblinded and interventional, where all patients who fulfil eligibility requirements will be assigned to receive CAB LA + RPV LA and complete assessments as per the study protocol.

For SSPs, the study is two-arm, unblinded, non-interventional and cluster-randomized at the country level. Sites within a given country will be randomized to either the Standard (Arm-s) or the Enhanced (Arm-e) implementation arm. The two arms will involve the provision of overlapping but distinct types of implementation components that are designed to assist in the local implementation of the study drug at each site. Arm-s represents the traditional provider support by a medical science lead and product materials. Arm-e models a higher level of provider support with added face to face meeting, trainings, and additional touchpoints for administration of CAB LA + RPV LA. The study will evaluate both qualitative and quantitative measures across arm, clinic type, provider type, and country to determine the most effective implementation strategies and to identify barriers and facilitators (including solutions). Clinical data will be collected to monitor safety and efficacy.

2.2. Background

2.2.1. Treatment Background

[figure not shown]
The treatment of HIV-1 infection has advanced since the first oral antiretroviral agent (zidovudine, AZT) was approved for the treatment of HIV-1 infected individuals in 1987. Newer antiretrovirals are more potent, better tolerated and have enabled the formulation of multiple regimens that can provide viral suppression with a single tablet once daily. Moreover, clinic visits for laboratory monitoring have become less frequent; current standard of care for virally suppressed patients is a clinic visit with laboratory every 3-6 months. While there have been major advances in the field of HIV therapeutics, tolerability, long term safety concerns and adherence remain significant limitations to treatment success. Consistent lifetime daily adherence is difficult for many patients, reducing effectiveness of these treatments (DHHS, 2019). Moreover, intermittent compliance can result in HIV drug resistance, with subsequent regimens being more complicated to construct.

Long-acting injectable versions of drugs are being developed to enable therapy with infrequent dosing injection and represent an emerging paradigm for the treatment of HIV infection. CAB is a potent integrase inhibitor that possesses attributes that allow formulation and delivery as a long-acting product. RPV, also formulated as a LA product, is a diarylpyrimidine derivative and a potent non-nucleoside reverse transcriptase inhibitor (NNRTI) with *in vitro* activity against wild type HIV-1 and select NNRTI-resistant mutants. A two-drug regimen with CAB LA plus RPV LA (CAB LA + RPV LA) may offer many potential advantages over daily oral regimens including infrequent dosing that decreases the daily reminder to patients of their HIV status, decreased development of viral resistance due to intermittent compliance with oral agents and overall treatment satisfaction in virologically suppressed patients. Results to date have demonstrated the efficacy of a two-drug regimen of CAB LA + RPV LA as maintenance therapy with several on-going Phase 2 and 3 studies including LATTE-2, ATLAS, FLAIR, and ATLAS 2M [Margolis, 2017].

2.2.2. New Treatment Paradigm

This new HIV treatment will require changes to the current standard of prescribing oral antiretroviral therapies to prescribing and delivering a complete antiretroviral long-acting injectable regimen. This new treatment paradigm will require more frequent visits by patients to see a provider and receive injections, as well as potentially require greater resources in the clinical setting to administer the injection. As this is a new treatment modality for people living with HIV (PLHIV), it is important to understand how to optimize the delivery of CAB LA + RPV LA from the perspective of PLHIV, health care providers (HCP) and the healthcare system. Without a plan that meets the needs of all three of these groups, the implementation of CAB LA + RPV LA may be hindered. Concerns raised about chronic dosing injections include overburdening the health-care system. Additionally, there are concerns that patients will miss scheduled injections also resulting in a fear of inadequate antiretroviral therapy coverage.

The need for pragmatic data is essential to fully understand the barriers and facilitators for delivery of this treatment. The effectiveness of CAB LA + RPV LA has been documented in several Phase 2b studies with several larger Phase 3 studies (ATLAS, ATLAS-2M and FLAIR) and resulted in positive patient-level outcomes. It is critical to understand *how* to effectively implement this treatment to ensure optimal impact on healthcare service system- and patient-level outcomes. Unfortunately, 50% of effective interventions do not make it into routine care, not as a result of lack of effectiveness, but rather a lack of understanding of the contextual factors that make uptake challenging (Bauer, 2019).

(Bauer, 2019).

Implementation science has been deployed across numerous contexts, including the area of long-acting injectable antipsychotics for the treatment of schizophrenia (Kishimoto, 2013). The use of a long-acting antipsychotic injectable medication was a significant paradigm shift within the psychiatric community and required work to address both organizational and attitudinal barriers by physicians in clinical practice. Implementation research began in this area to understand the barriers needed to overcome and support the use of the long-acting injectable, but only after identifying significant difficulties in uptake. The lag between the availability of this injectable and the use of implementation research hindered the rate of adoption and reach of this innovative treatment. Examples where implementation science has been used to improve availability of evidence-based treatment in routine care includes a range of fields including HPV vaccination, cancer care, primary care weight management, and psychotherapy (Soi, 2019; Leeman, 2019; Smith, 2018; Triplett, 2020).

Within HIV, implementation science has lagged behind other fields. The low uptake of pre-exposure prophylaxis (PrEP) is a prime example where implementation science could have supported a greater uptake in the real world given the significant gap between the number of people recommended for PrEP and the actual number receiving it (hiv.gov; Partners Scale-up Ref). The lag time between availability of an innovation, identification of barriers to translation into the real world through implementation research, and the use of implementation strategies can impact the rate at which the HIV epidemic can be ended. Implementation science can help maximize the impact of an innovation when used proactively in early stages of intervention development and availability.

This study is the first of its kind to examine the use of CAB LA + RPV LA by both healthcare professionals and patients in different clinical care settings in Europe. Incorporating implementation research into CAB LA + RPV LA across Europe will increase the impact of the treatment at a population level. Data in implementation science and CAB LA + RPV LA is in its infancy. While CUSTOMIZE (209493) is an ongoing initial implementation study of CAB LA + RPV LA, results remain forthcoming and only focused on sites in the United States.

Clinical care is a dynamic environment with multiple factors impacting an interventions' success or failure. The proposed approach in this study allows for each site to operate as close to routine care as possible while helping address barriers, supporting facilitators of, and implementation of CAB LA + RPV LA. **Barriers** are any perceived factors that obstruct a site from successfully implementing CAB LA + RPV LA. For example, this might include availability of clinical staff to accommodate additional appointments, lack of injection training or patient education and support. **Facilitators** are any perceived factors that enable successful implementation of CAB LA + RPV LA. Examples of facilitators include existing systems for cold chain storage, previous injector experience with intramuscular injections, and existing patient support applications or communication channels to assist in adherence and education. Despite different overarching components that define the arm-e and arm-s, both strategies leverage existing facilitators and aim to overcome barriers to successful implementation of CAB LA + RPV LA.

Additional examples of implementation strategies at a country level to address identified barriers in the arm-e may be found in a supplemental implementation science handbook.

